2.7 Subgroup analyses

No subgroup analyses will be performed.

3 Changes to planned analyses

It has been decided prospectively that a per-protocol analysis will not be performed since the study focuses on long-term safety monitoring for which the safety set will be the primary analysis population.

4 Statistical analyses

4.1 General considerations

Data transfer from EP00-401

Some information for analyses planned in the protocol is not provided in the CRF of this follow-up study, but in the CRF of study EP00-401 only. Therefore, the following variables provided in the CRF of EP00-401 will be transferred to this study:

- age at final visit
- gender and race
- physical examination and pubertal status at final visit
- height, height Standard Deviation Score (SDS) at final visit
- weight and BMI, BMI SDS at final visit
- fasting plasma glucose, OGTT results, fasting plasma insulin, HbA_{1C} at final visit
- IGF-I, IGFBP-3, IGF-1 SDS, and IGFBP-3 SDS at final visit
- anti-rhGH antibody testing at final visit
- safety lab at final visit
- blood pressure and pulse at final visit
- exposure to study drug

Data of study EP00-401 will be transferred to EP00-402 on the same date the EP00-402 database is locked. In general, analysis data (i.e. data created for the analysis of EP00-401) will be transferred not the original CRF data.

Study days, baseline and visits

Study days are defined as date of assessment minus date of baseline visit.

Baseline is defined as final visit of study EP00-401. If no date of final visit is available, the date of F0 baseline visit of study EP00-402 will be used instead.

Analyses by visits will be based on CRF visits, i.e. F1 Month 6, F2 1 Year, F3 5 Years, and F4 10 Years/Final. The CRF visit F4 10 Years/Final will be presented as EOS (termination visit).

Conversion factors for laboratory parameters

In order to harmonize laboratory results by using the same units, some laboratory results will be converted. Corresponding conversion factors will be listed by parameter and will provide CRF unit, SI unit and conversion factor. If albumin is given in %, the respective values will be converted to g/l using total protein values.

[figure not shown]

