2.1 Study documents and general considerations

This document describes the procedures and conventions to be used in the final analyses with data of all patients who were included into study EP00-402.

The study is based on the

- study protocol V 1.0, dated 16 Mar 2007,
- Amendment no. 01, dated 12 Mar 2012 incorporated into protocol v 1.0 leading to protocol v 2.0, dated 12 Mar 2012,
- Amendment no. 02, dated 9 May 2012 incorporated into protocol v2.0 leading to protocol v3.0, dated 9 May 2012,
- Amendment no. 03, dated 6 Jun 2013 incorporated into protocol v3.0 leading to protocol v 4.0, dated 6 Jun 2013,
- Amendment no. 04, dated 14 July 2014 incorporated into protocol v4.0 leading to protocol v5.0, dated 14 July 2014.

This study was terminated by the sponsor [REDACTED] Following decision of [REDACTED] study termination all patients were called in for a last visit (documented on the final visit page of the case report form (CRF)).

Raw data listings, summary tables, graphs and statistical tests will be generated by means of the program SAS 9.3 or higher.

The following descriptive statistical parameters will be shown in summary tables

- Continuous variables: n (valid cases), n (missing data), mean, median, standard deviation (SD), min, max, quartiles
- Categorical variables: Count and percentage of category. Percentages are routinely based on the total category count excluding the missing category if not otherwise mentioned. Percentages showing a rate relative to the total number of patients in this group are given in special tables (e.g. Adverse Event (AE) tables). Footnotes will specify the percent basis.

For continuous variables, if not otherwise specified, mean, median and quartiles will be reported to one decimal place greater than the precision of data as collected. Standard deviation will be

presented in two decimal place greater than the data and minimum/ maximum values will be reported with the same precision, as they were collected. This rule is only valid if values are not converted for the summary.

Generally, percentages will be displayed in the format xx.d, i.e. one decimal place will be shown; if the calculated percentage is 100, no decimal is required (i.e. 100% and not 100.0%). If the count is zero no percentage needs to be shown.

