2.3 Endpoints

2.3.1 Primary Endpoint

The development of diabetes is the primary endpoint of the study and is evaluated on the basis of the carbohydrate metabolism (fasting plasma glucose (FPG) and oral glucose tolerance test (OGTT)).

Specifically of interest is, number and percentage of patients developing overt type II diabetes mellitus after the end of GH treatment, characterized by fulfilment of the following criteria:

- FPG \geq 126 mg/dl (7.0 mmol/l) during blood sampling and/or during OGTT
- 2-h plasma glucose \geq 200 mg/dl (11.1 mmol/l) during OGTT

Documented confirmation on diagnosis of diabetes mellitus by investigator during OGTT will also be considered to qualify incidence of elevated glucose values as development of overt type II diabetes mellitus.

Fasting plasma glucose as well as an OGTT will be measured at baseline (i.e. final visit of EP00-401), 6 months, 1, 5 and 10 years after the end of treatment.

Additional criteria – carbohydrate metabolism

Additionally, long term effect of growth hormone (GH) treatment on carbohydrate metabolism is also assessed by

- Change from baseline in FPG, baseline and 2hr plasma glucose (during an OGTT), fasting plasma insulin and glucose glycosylated hemoglobin (HbA_{1C}) at 6 months, 1, 5 and 10 years after the end of treatment.

- **Insulin resistance** will be estimated at baseline, 6 months, 1, 5 and 10 years after the end of treatment, using both the homeostasis model assessment (HOMA; Matthews et al. 1985) and quantitative insulin sensitivity check index (QUICKI; Katz et al. 2000):

$$\text{HOMA} = \frac{\text{fasting insulin } (\mu\text{U/ml}) \times \text{fasting glucose (mg/dl)}}{405.41^*}$$

*use constant 22.5 instead of 405.41 if glucose concentration is reported in mmol/L

$$\text{QUICKI} = \frac{1}{\log \text{fasting insulin } (\mu\text{U/ml}) + \log \text{fasting glucose (mg/dl)}}$$

Implausible insulin or glucose values will be excluded, i.e. Glucose values below 0.1 mmol/L and insulin values below 0.1 pmol/L will not be used for the calculation of HOMA and QUICKI.

Potential of GH-treatment induced insulin resistance will be captured through change from baseline in HOMA and QUICKI at 6 months, 1, 5 and 10 years after the end of treatment

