2.3.2.2 Efficacy Endpoints

Secondary efficacy endpoints of this study include:

- **Pharmacodynamic endpoints** Change from baseline in hGH-induced serum IGF-I and serum IGFBP-3 levels, as well as the respective serum IGF-I level SDS and serum IGFBP-3 level SDS, at 6 months, 1, 5 and 10 years after the end of treatment. For further details on the calculation/derivation of the serum IGF-I level SDS and the serum IGFBP-3 level SDS, see Section 5.3.
- **Height measurement related endpoints** include height, height SDS, final height, and final height SDS. Height will be measured according to the usual clinical practice at all visits including baseline, 6 months, 1, 5, and 10 years after the end of treatment. Height SDS will be calculated/derived from the height measurement for all visits including baseline, 6 months, 1, 5, and 10 years after the end of treatment. For further details on the calculation/derivation of height SDS, see Section 5.2. The final height is defined as the respective maximum value of height. Final height SDS is the respective SDS value for maximum value of height. For further details on the calculation/derivation of final height and final height SDS, Section 5.2.

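### The EOS column pools last visits made at varying times after GH treatment, so no table isolates the 10-year change from baseline

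*SAP*

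**What the plan says.** Section 2.1 reports that the sponsor terminated the study and that, afterwards, "all patients were called in for a last visit (documented on the final visit page of the case report form (CRF"). It attaches no condition on how long each patient had been off treatment.

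Section 4.1 sets the rule for all by-visit output: "Analyses by visits will be based on CRF visits, i.e. F1 Month 6, F2 1 Year, F3 5 Years, and F4 10 Years/Final". It then adds: "The CRF visit F4 10 Years/Final will be presented as EOS (termination visit"). A time axis exists, since "Study days are defined as date of assessment minus date of baseline visit", but no rule uses it to place an assessment in a visit.

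The endpoint definitions keep the full schedule. Section 2.3.1 specifies "change from baseline in HOMA and QUICKI at 6 months, 1, 5 and 10 years after the end of treatment", and the same time points for glucose, insulin and HbA1c. Section 2.3.2.1 does so for safety laboratory values, vital signs, weight and BMI. Section 2.3.2.2 does so for IGF-I and IGFBP-3, including "serum IGF-I level SDS and serum IGFBP-3 level SDS, at 6 months, 1, 5 and 10 years after the end of treatment".

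Section 3, on changes to planned analyses, mentions only that the per-protocol analysis is dropped.

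**The concern.** The F4 page serves two purposes: the scheduled 10-year visit and the last visit after termination. Because tables follow the page and not the date, the EOS column is driven by the calendar. Each patient contributes whatever follow-up had been reached when the study stopped. As an illustration only, a patient seen 18 months after treatment and one seen 9 years after would be averaged in the same cell.

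The metabolic and IGF endpoints are there to show what happens at a known time after GH is stopped. Patients are still maturing during follow-up, which the SAP recognises by summarising Tanner stage by visit (4.4.2). An EOS mean of insulin, HOMA, QUICKI or raw IGF-I then reflects the mix of follow-up lengths and ages at termination as well as any lasting effect of treatment. The analysis is descriptive, so no model adjusts for time: the tables are the result.

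The point concerns the continuous carbohydrate, IGF, laboratory, vital-sign and BMI endpoints. It does not concern how the diabetes count is expressed.

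**Working it through.** The SAP states no figure that could be reproduced: no sample size, no follow-up distribution and no termination date. The check is a mapping of visits to columns.

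**Step 1. Where each assessment goes under 4.1**

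| Assessment | CRF page | Column | Time since treatment known from the table? |
|---|---|---|---|
| 6-month visit | F1 | Month 6 | Yes, nominally |
| 1-year visit | F2 | 1 Year | Yes, nominally |
| 5-year visit | F3 | 5 Years | Yes, nominally |
| True 10-year visit, if any | F4 | EOS | No |
| Last visit after termination, at any time | F4 | EOS | No |
| Last visit near year 5, no F3 page | F4 | EOS, absent from 5 Years | No |

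**Step 2. Compare with the endpoints.** Sections 2.3.1, 2.3.2.1 and 2.3.2.2 ask for values at 6 months, 1, 5 and 10 years. The first three each have a column. Year 10 has none of its own. Sections 4.6.2, 4.7.1.2, 4.7.1.4 and 4.7.2.1 all analyse by visit, so the rule in 4.1 reaches all of these endpoints.

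**Step 3. What the EOS mean estimates.** Let p be the share of EOS values that are true 10-year values, m10 their mean, and mE the mean of the earlier termination visits. Then

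EOS mean = p × m10 + (1 − p) × mE.

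This equals m10 only if p = 1 or mE = m10. If p = 0, the column carries no 10-year information. The SAP gives no way to know p, so the range is 0 to 1.

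**Step 4. What the dates allow.** Protocol V1.0 is dated 16 Mar 2007. If no baseline preceded that date, the earliest 10-year point is 16 Mar 2007 + 10 years = 16 Mar 2017. The last listed amendment, 14 July 2014, is about 7.3 years after V1.0. The assumption may fail: 4.1 defines baseline as the final visit of EP00-401, and nothing shown says that visit could not have come before the EP00-402 protocol. These dates therefore illustrate the possibility of few or no 10-year values; they do not establish it.

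**Step 5. Can the time be recovered elsewhere?** Section 4.5.2 summarises final visit date − baseline date + 1 over all patients, converted to months. Section 4.6.2 lists sample date or day per patient for the carbohydrate data. Neither places a time beside the values averaged in a given EOS cell, where the patients with a usable result can differ from one parameter to the next.

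**The case against.** Tabulating by CRF page with an EOS column is a workable choice for a descriptive study that stopped early. The label matters: the column is called EOS, not 10 years, so nobody is told that it holds 10-year values. The exposure summary in 4.5.2, with the descriptive statistics listed in 2.1, comes close to giving the median and range of follow-up at the last visit, and the listings allow reconstruction for the carbohydrate data. IGF-I SDS and IGFBP-3 SDS are standardised for age and gender (5.3), and BMI SDS is analysed beside BMI, so the argument from age is weaker there.

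All of this stands as mitigation. It does not supply the defined 10-year result or say that it has been given up. The age concern applies mainly to insulin, HOMA, QUICKI and raw IGF-I; differing time off GH affects the SDS values as well.

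A reader might also infer more than the SAP supports:

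- **That the 5-year change cannot be read.** It can: F3 has its own column. It may only be incomplete, and the number of final-page visits near year 5 without an F3 page is unknown.
- **That termination visits are certainly mixed with true 10-year visits.** The redacted termination date leaves open whether there were any.
- **That there were certainly no 10-year visits.** This does not follow either, for the reason given with the date arithmetic.

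**Conclusion.** The concern holds in a limited form. Under 4.1, EOS pools assessments at varying times since the end of GH treatment with any true 10-year visits. The 10-year change from baseline is not isolated in any table, and Section 3 does not say so.

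This is true whatever the number of 10-year visits. If there are some, they are hidden among earlier ones. If there are none, the 10-year endpoint cannot be estimated and the SAP should state that. The 5-year column is valid as far as it goes.

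The size of any distortion cannot be given. It depends on the spread of follow-up at termination and on how far each parameter changes with age and time off GH, and the SAP provides neither. The conclusion rests on reading the final visit page in 2.1 as the F4 10 Years/Final page in 4.1, which their labels support. It is a correction worth making, not a defect that invalidates the analysis.

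**What to change.** - **Section 4.1:** assign a final-page assessment to the 5-year or 10-year analysis window when its time since end of treatment falls within limits stated before database lock. Say which date starts the clock, last dose or baseline visit. Add a rule for two assessments in one window, for example the one closest to the target time.
- **EOS column:** keep it, labelled as last observation, and show n, median and range of years since end of treatment for the values summarised.
- **Section 3:** state that EOS replaces the 10-year time point where the 10-year window is empty or nearly so, with a pre-stated minimum n, and that no 10-year conclusion is then drawn.

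The cost is revised wording and one derivation step on visit dates already collected. The drawback is a few extra columns, some with small n.

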4.2 Disposition of patients

Number of patients enrolled in the study will be summarized by site and for overall population along with number of patients at different visits. A summary for number and percentage of patients included in each analysis set will be provided separately. Patients prematurely discontinuing the study will be descriptively summarized by presenting number and percentage of such patients both in overall population and also by primary reason for discontinuation. Premature study discontinuations will also be listed at a patient level quoting site number and primary reason of discontinuation.

4.3 Protocol deviations

Number of protocol deviations as well as the number and percentage of patients with protocol deviations will be summarized overall and by protocol deviation category and classified reason for exclusion/protocol deviation for all enrolled patients. The summary of reported protocol deviations will be presented according to the following categories as agreed during data review meeting –

- Inclusion/exclusion criteria
- Withdrawal/ termination criteria met, but subject not discontinued
- Failure to perform key procedures
 - Lab values not taken
 - Study assessment not done
 - visit window (deviation from protocol specified visit schedule)
- GCP-related deviation

In addition all protocol deviations will be listed on a subject level.

According to the decisions made during the data review meeting prior to DBL, following patient will be excluded from the appropriate analyses sets with details as below:

Table 4-1 Summary of patients excluded from analysis set(s)

Patient	Analysis set excluded from	Reason for exclusion
[REDACTED]	SAF/ FAS	[REDACTED]

4.4 Demographics and baseline characteristics

4.4.1 Demographics

Following demographic and baseline characteristics are summarized for patients in full analysis set (FAS).

Continuous variables: Age at baseline, baseline height, baseline height SDS (for further details: Section 5.2), baseline weight, BMI and BMI SDS at baseline (for further details: Section 5.1). BMI is calculated by [weight in kg] divided by [height in m]².

Categorical variables: Gender, ethnic origin

These demographic/ baseline characteristics will also be listed at a patient level including informed consent dates/days of first legal guardian, second legal guardian and child.

4.4.2 Pubertal status

The number and percentage of pubertal patients evaluated at each Tanner stage (Tanner Stages 1-5) will be summarized by gender and visit.

4.4.3 Concomitant medication

Information on administration of any medications, except investigational medicinal products, should have been reported in the appropriate section of the CRF, along with dose information, dates of administration and reason for use. Any diagnostic, therapeutic or surgical procedure should have also have been recorded, including the date, indication, descriptions of the procedure and clinical findings.

Concomitant medication will be coded according to WHO-DRL. For version and used update strategy for coding see coding guideline for this study. All documented concomitant medication data will be summarized separately by Anatomical Therapeutic Chemical (ATC) term (level 2) and preferred term, providing the number and % of patients to whom medication was administered. This summary will be prepared for the FAS analysis set.

4.5 Exposure to study drug

4.5.1 Treatment exposure

The extent of exposure in the EP00-401 study will be analyzed using descriptive statistics.

According to the SAP for interim analysis of study EP00-401 exposure will be assessed as follows:

The patient's exposure to study drug will be calculated from the date of first dose to the date of last study drug administration for patients that prematurely discontinued or completed the study and presented in months as a decimal.

If date of last study drug administration is missing completely or only a year is given and the patient has discontinued or completed the study, then the date the patient discontinued or completed the study shall be used instead. If date of last study drug administration was given only partial (i.e. month and year given), the first date of the month will be assumed as last administration date. Study drug exposure in days will be converted to study drug in months as follows:

- Exposure (months) = Exposure (days)*12/365.25.

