4.5.2 Study exposure

Study exposure for patients entering the observation period for EP00-402 study is calculated as:

Study exposure (days) = Date of final visit – Date of baseline visit +1

Study exposure (days) will be converted to months as treatment exposure and will be summarized in a similar manner.

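### The rules for an incomplete last-dose date in SAP 4.5.1 can place the last dose outside the recorded year or before the first dose

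*SAP*

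**What the plan says.** SAP section 4.5.1 defines treatment exposure in EP00-401 as the time "calculated from the date of first dose to the date of last study drug administration", presented in months. It takes its rules from the SAP for the interim analysis of that study. For incomplete last-dose dates it sets two rules:

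- **Year only, or nothing recorded.** Both situations get the same treatment once a patient has left or finished EP00-401: "then the date the patient discontinued or completed the study shall be used instead". Nothing requires the substitute date to lie in the recorded year.
- **Month and year recorded.** "the first date of the month will be assumed as last administration date". Nothing compares that day with the first dose.

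Days are converted by "Exposure (months) = Exposure (days)*12/365.25". On use, the section says: "The extent of exposure in the EP00-401 study will be analyzed using descriptive statistics".

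**The concern.** An imputed date should agree with whatever part of the date was recorded and should give a possible duration. Neither rule ensures this. The first discards a known year. The second can put the last dose before the first. The two rules also err in opposite directions: the less complete record gets the latest possible date and the more complete record gets the earliest. The summarised duration then depends partly on how much of the date was written down.

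At stake is the accuracy of the SAP's summary of how long patients received growth hormone, in a study whose primary objective (section 2.2) is the long-term effect of that treatment.

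**Working it through.** The SAP states no figure to reproduce, so the check is date arithmetic. The inputs are the two rules and the conversion factor 12/365.25, all from section 4.5.1. One assumption is added: dosing does not continue after discontinuation or completion. All dates below are illustrative.

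**Year-only rule.** The error is the substitute date minus the true last dose. The true date can be any day of the recorded year up to discontinuation.

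- Recorded year 2009, left on 15 March 2010. The latest compatible last dose is 31 December 2009. The smallest error is 31 + 28 + 15 = 74 days, and 74 × 12/365.25 = 2.4 months.
- The earliest compatible last dose is 1 January 2009. The largest error is 364 + 74 = 438 days, or 14.4 months.

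For recorded year 2010 and different leaving dates:

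| Left study | Overstatement, days | Months |
|---|---|---|
| 30 Jun 2010 | 0 to 180 | 0 to 5.9 |
| 31 Dec 2010 | 0 to 364 | 0 to 12.0 |
| 31 Mar 2011 | 90 to 454 | 3.0 to 14.9 |
| 31 Dec 2011 | 365 to 729 | 12.0 to 24.0 |

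If the patient left within the recorded year, the lower limit is zero and the substitute date is compatible with the record. If the patient left in a later year, the lower limit is above zero: the date is known to be wrong and the overstatement is certain.

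**Month-known rule.** The error is day 1 minus the true day, so it runs from 0 to −30 days (0 to −0.99 months). If the true day is uniform over a 365-day year, the mean shortfall is found as follows:

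- A month of L days contributes 0 + 1 + … + (L − 1) = L(L − 1)/2 days.
- Sum: 7 × 465 + 4 × 435 + 378 = 5,373.
- Mean: 5,373/365 = 14.7 days, and 14.7 × 12/365.25 = 0.48 months.

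Negative values are possible. With a first dose on the 20th and a last dose later in the same month, day 1 gives 1 − 20 = −19 days, or −0.62 months.

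**One patient under each rule.** First dose 1 January 2006, true last dose 20 December 2010, left on 31 March 2011. True exposure is 1,814 days, or 59.60 months.

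| Last-dose date used | Days | Months | Error, months |
|---|---|---|---|
| Month known, SAP rule (1 Dec 2010) | 1,795 | 58.97 | −0.62 |
| Year only, SAP rule (31 Mar 2011) | 1,915 | 62.92 | +3.32 |
| Month known, mid-month (15 Dec 2010) | 1,809 | 59.43 | −0.16 |
| Year only, limited to recorded year (31 Dec 2010) | 1,825 | 59.96 | +0.36 |

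**The case against.** The strongest case for leaving the text alone is that nothing else depends on it. Treatment exposure is only described. Adverse event rates per patient-year (section 4.7.1.3) use study exposure from section 4.5.2. The diabetes endpoint (section 4.6.1) does not use exposure, and no subgroup analyses are planned (section 2.7). Keeping the parent study's derivation for parent-study exposure is also a reasonable wish for consistency. Section 4.1 lists exposure among the items transferred from EP00-401, in general as analysis data, so it may arrive already derived. All of this stands, and it limits the point to a minor one.

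It is also fair to say that day 1 of a known month is a convention. The last day of the month would be just as one-sided, up to 30 days too long instead of too short. The downward lean alone is therefore not an error. The missing floor at the first dose is.

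Two stronger readings are tempting but not supported:

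- **A one-day inconsistency.** Section 4.5.2 ends its formula with "Date of baseline visit +1", and a reader might infer that treatment exposure omits the extra day, so that a single dose counts as 0 months. Section 4.5.1 gives no formula for days, only a start and an end, which can be read inclusively. One day is 12/365.25 = 0.03 months in any case.
- **A concentration in early discontinuers.** The SAP does not say which patients have incomplete dates, and the rules cover completers as well.

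**Conclusion.** The point holds as a minor defect of specification. Applied as written, the year-only rule contradicts the record whenever the patient left in a later year than the one recorded, and exposure is then certainly overstated (at least 74 days in the 2009/2010 example). The month-known rule never overstates, understates by 0.48 months on average, and allows a negative duration.

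This rests on dosing not continuing after discontinuation or completion and, for the average, on stop days being uniform over the month. The number of patients with incomplete dates is not given. The cross-year and negative cases are outcomes that the rules permit, not events shown to have occurred. A reader might infer that the safety results are biased. They are not affected, because only the descriptive summary of treatment exposure uses these dates.

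**What to change.** Amend section 4.5.1 as follows:

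1. **Year only:** use the earlier of the discontinuation or completion date and 31 December of the recorded year. This changes nothing for patients who left within that year. It remains the latest compatible date, so it still leans upward, but it no longer contradicts the record.
2. **Month and year:** use a neutral day such as mid-month. The mean true day under the uniform assumption is 14.7 + 1 = 15.7, so day 15 leaves an average shortfall of about 0.7 days (0.02 months).
3. **All imputed dates:** do not let them fall before the first dose or after discontinuation or completion.
4. **Reporting:** footnote the exposure table with the number of imputed dates.

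A fully missing date can stay as it is, since there is no recorded part to contradict.

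The cost is a few sentences and a few lines of code. There is a small downside: because section 4.1 plans to transfer analysis data, the recorded partial dates may also have to be transferred. Values may differ slightly from those reported for EP00-401, which the same footnote can explain.
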